These methods, however, may be limited by imprecision, limited ESWL availability for PD stone therapy in the US, requirement of multiple treatment sessions, and decreased efficacy in removing larger, impacted stones.^{9, 10} From a practical standpoint, the need to frequently outsource ESWL to urologists limits the ability of gastroenterologists to control the timing of these sessions and assess efficacy while potentially increasing patient costs, time commitment, and use of general anesthesia.¹¹ If ineffective in stone clearance, surgery remains a last-resort option that is associated with high morbidity (18-53%) and mortality (0-4.55%).¹² The introduction of per oral pancreatoscopy, or direct endoscopic visualization of the PD, has enabled targeted intraductal therapy, including electrohydraulic lithotripsy (**EHL**) and laser lithotripsy (**LL**) for these stones.¹³ None of these treatment methods have been studied in prospective trials and there is a lack of comparative data between ERCP techniques and ESWL in removing stones, whether they improve pain and quality of life, and reduce opiate use along with assessing financial costs. There is, therefore, a *critical need* to compare the efficacy of per oral pancreatoscopy-guided lithotripsy (**PPL**) with ESWL and determine which therapy provides better outcomes with a goal of less procedures and that is more cost-effective in removing difficult PD stones. Without such information, the treatment of main pancreatic duct stones associated with chronic pancreatitis will likely remain limited anecdotal and consisting of retrospective case series.

Within the field of pancreatology, there exists legitimate equipoise regarding which treatment is more effective in removing pancreatic duct stones. ESWL has been performed for a longer period of time with a meta-analysis including 27 studies and 3189 patients demonstrating a 70% complete duct clearance rate with the use of ESWL.¹⁴ There have been far fewer studies involving PPL with a recent meta-analysis involving 302 patients in 10 studies found a 86% success rate in stone clearance.¹⁵ Importantly, a randomized study comparing the two techniques has not been performed and the only randomized study

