Statistical Analysis: Comparison of technical success rate, defined as the rate of complete clearance of PD stones, between PPL and ESWL will be performing using the chi-squared test or Fisher's exact test. Secondary outcomes including adverse event (both overall and serious adverse event) rates, procedure length, and number of procedures will be compared using a chi-square test or Fisher's exact test for categorical variables and the Student's t test will for continuous variables. A p value <0.05 will be considered significant. In the primary analysis, all results will be analyzed under an intention-to-treat protocol. A per-protocol (secondary) analysis will also be performed where the technical success will be attributed to the combination of modalities resulting in achieving the primary outcome should cross-over occur.

To identify predictors for technical success, a multivariable logistic regression will be performed incorporating variables that were associated ($p<0.2$) with technical success on univariate analysis.

In terms of secondary outcomes, change in PANQOLI scores, VAS scores, and opiate daily doses will be compared between subjects in the PPL group and ESWL group. Additional outcomes to be measured include stone recurrences and number of chronic pancreatitis-related hospitalizations during the follow-up period. Should cross- over occur, under the primary (intention-to-treat) analysis, the outcomes will be attributed to the initially randomized intervention. In the secondary (per-protocol) analysis, the outcomes will be attributed to the combination of treatments resulting in technical success. A subgroup analysis will also be performed on patients who achieved only partial stone clearance (thus considered a treatment

failure) in the above-mentioned outcomes. Comparisons will be made using a chi-squared test or Fisher's exact test for categorical variables and the Student's t test for continuous variables. Paired t tests will be performed to evaluate individual changes within each arm. A p value <0.05 will be considered significant.

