Power analysis: A large meta-analysis by Moole et al found a complete stone clearance rate of 70% in patients who received ESWL in conjunction with ERCP.¹⁴ In contrast, the largest studies examining pancreatoscopy-guided lithotripsy methods have found complete stone clearance rates ranging from 83-99%.^{6,17} Using a conservative stone clearance rate of 90% for pancreatoscopy- guided lithotripsy, a sample size calculation was performed using a two-sided test with 80% power and significance (α) of 0.05. This demonstrated the need for 124 subjects total, with 62 in each arm. Accounting for an expected dropout rate of 20%, the sample size needed would be a total of 150, or 75 subjects in each arm.

10. Data and safety monitoring plan

A Data and Safety Monitoring Board (DSMB) will be established to monitor the data and safety of this project. A DSMB will be appointed by the study team and will include at a minimum: A senior faculty member clinician with substantial research experience within the Division of Gastroenterology and Hepatology at the University of Colorado who is not involved in the study, and will serve as the group leader, a statistician, and a senior gastroenterologist from a non- participating academic institution. The DSMB will meet every six months. DSMB meetings will be only open to designated DSMB staff and other individuals who have been approved to have access to unblinded data. Any recommendations for alteration or termination for part or all of the trial shall be based on consideration of the accumulating data in the context of totality of evidence. Specific statistical monitoring guidelines for safety and efficacy concerning the primary and secondary endpoints will be developed in cooperation with the DSMB.

10.1 *Definition of AEs, serious AEs, and unanticipated problems*

AEs are defined as any undesired, harmful, or pathological change in a patient as indicated by signs, symptoms, or laboratory changes that occur in association with the use of the trial interventions, whether considered intervention-related or not. This definition includes intercurrent illness or injuries, exacerbation of existing conditions, psychological events, psychosocial events, and AEs as a result of the study intervention. All endoscopic AEs will be defined and classified as recommended by the American Society for Gastrointestinal Endoscopy (ASGE).²⁰

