All serious AEs that occur from initiation of the study to 14 days post final intervention are to be reported immediately (within 24 hours) using the electronic data collection system. All serious AEs will then be immediately relayed to the PIs. The PIs will first review the AEs to: 1) ascertain the seriousness, 2) ascertain the relationship between AE and intervention, 3) verify that all data are complete, and 4) follow-up with the specific site for incomplete data and/or data clarification. The PIs will then submit the AEs to the DSMB, who will then review the AEs to confirm the findings of the PIs.

All AEs from ESWL are ESWL-related. PPL is part of the ERCP procedure. Most AEs in this group will be related to the ERCP procedure itself. A potential rare AE specific to PPL (EHL or LL) is ductal perforation from the lithotripsy fiber and will be noted by the investigator. The investigator will determine the relationship of an AE specific to a lithotripsy device used to fragment the stones.

10.3 *Monitoring of Data*

The DSMB will be responsible for data and safety monitoring. All primary and secondary outcomes as well as data integrity and study progress along with all AEs will be reviewed by the DSMB.

The DSMB will meet at least twice a year to review the data mentioned above. These meetings will every six months.

An interim analysis will be performed at the halfway point of enrollment, which is expected to be at the 75th patient. Should the interim analysis reveal an unexpected accumulation of AEs or a clear superiority of one lithotripsy method over the other, the DSMB may recommend stopping the study, which will be reported to the PIs, IRB and the funding agency.

The DSMB will include at a minimum the following individuals:

- [name]: Gastroenterologist, University of Colorado
- [name]: Hepatologist, University of Colorado
- Biostatistician: Non-study Statistician
- [name]: Gastroenterologist, Beth Israel Deaconess Medical Center

11. Feasibility/Recruitment Plan/Materials

The power analysis suggests that a total of 150 participants will need to be enrolled to achieve sufficient statistical power to compare the two lithotripsy methods. With a total of 8 recruitment sites, we anticipate complete enrollment within 5 years and with a follow-up of 12 months/patient post completion of treatment, the study is anticipated to be completed within 6 years.

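### Enrolling 150 does not keep the required 124 evaluable patients at the stated 20% dropout (120 remain; 155 to 156 would be needed), though the power cost is small

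*Combined protocol and SAP*

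**What the plan says.** The power analysis paragraph of Section 9 (Data Analysis Plan) takes its ESWL rate from a meta-analysis that found "a complete stone clearance rate of 70% in patients who received ESWL in conjunction with ERCP". For PPL it cites "complete stone clearance rates ranging from 83-99" per cent and continues: "Using a conservative stone clearance rate of 90" per cent. With a two-sided 5% test and 80% power it reports: "This demonstrated the need for 124 subjects total, with 62 in each arm". It then inflates for dropout: "Accounting for an expected dropout rate of 20%, the sample size needed would be a total of 150, or 75 subjects in each arm".

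The Synopsis and Section 3 repeat 150 as the enrolment target. Section 11 says that "a total of 150 participants will need to be enrolled to achieve sufficient statistical power". No section gives another basis for 150.

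The statistical analysis paragraph of Section 9 names two possible primary tests without choosing: the comparison "between PPL and ESWL will be performing using the chi-squared test or Fisher's exact test". The primary analysis is by intention to treat.

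**The concern.** The dropout sentence presents 150 as the number that still leaves the required 124 after a 20% loss. If it does not, the plan's main sample-size statement is wrong on its own figures, and Section 11 passes it on as settled.

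The word *conservative* raises a lesser issue. It tells the reader that the assumed PPL rate sits towards the cautious end of the evidence, so that the calculation has some margin. The range in the preceding sentence does not show that.

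**Working it through.** **Inputs.** ESWL 70%, PPL 90%, two-sided alpha 0.05, power 80%, dropout 20%, 124 evaluable and 150 enrolled are all from the power analysis in Section 9. Allocation 1:1 is from Section 5.3. Equal loss in the two arms is my assumption.

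**1. Reproduce the 124.** Pooled two-proportion formula, no continuity correction:

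n per arm = [1.960 × √(2 × 0.80 × 0.20) + 0.842 × √(0.70 × 0.30 + 0.90 × 0.10)]² / (0.90 − 0.70)²

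= [1.960 × 0.5657 + 0.842 × 0.5477]² / 0.04 = 61.6, so 62 per arm and 124 in total. This matches the plan exactly and identifies its apparent method.

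**2. Check the dropout step.**

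- Remaining at 20% dropout: 150 × 0.8 = 120, or 60 per arm; 4 short of 124.
- Enrolment that keeps 124: 124/0.8 = 155. With equal arms, 62/0.8 = 77.5, so 78 per arm and 156 in total.
- Largest dropout at which 150 keeps 124: 1 − 124/150 = 17.3%.
- Likely origin of 150: 62 × 1.2 = 74.4, rounded up to 75 per arm. In total, 124 × 1.2 = 148.8.

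**3. Power cost for 70% versus 90%.** By the pooled normal approximation, power = Φ[(0.20 × √n − 1.960 × 0.5657) / 0.5477], with n per arm. The exact figures enumerate all outcomes of the two binomial samples.

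| Method | 62 per arm | 60 per arm |
|---|---|---|
| Pooled normal approximation | 80.3% | 78.9% |
| Uncorrected chi-squared, exact enumeration | 81.0% | 80.2% |
| Fisher's exact test, exact enumeration | 74.9% | 73.0% |

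By the plan's apparent method the loss is 80.26 − 78.94 = 1.3 points. If all 75 per arm have a primary outcome, the pooled approximation gives 87.2%.

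**4. The label on the 90%.** The midpoint of the cited range is (83 + 99)/2 = 91%. The assumed 90% is 1 point below the midpoint and 7 points above the lower end. With ESWL at 70%, a PPL rate of 83% gives about 39% power at 60 per arm and 47% at 75 per arm (pooled approximation).

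**The case against.** The strongest reply is that the slip hardly matters. By exact enumeration of the uncorrected chi-squared test, one of the two tests named, power at 60 per arm is still 80.2%. That stands, and it is why this is a minor correction. It does not rescue the sentence, which claims that 150 covers a 20% loss from 124. It also depends on the choice of test: the gap between chi-squared and Fisher's test is wider than the loss from the slip.

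A second reply is that dropout need not remove anyone from the primary analysis. Clearance is read from a pancreatogram at the end of treatment (Section 5.5), before the 1- to 24-month follow-up, and the analysis is by intention to treat. This stands in part. The plan inflates for dropout, so its own sum treats dropouts as lost, and the sum has to be checked on that basis. But the documents do not say how patients without a primary outcome enter the analysis, so 120 should not be the only basis for power. If every patient has an outcome, power is about 87%. If dropouts in both arms counted as failures, the rates would be 0.7 × 0.8 = 56% and 0.9 × 0.8 = 72%, with about 53% power at 75 per arm.

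A reader might also infer that 90% is contradicted by the documents, since Section 1 says "a recent meta-analysis involving 302 patients in 10 studies found a 86% success rate in stone clearance". They do not support that. The 86% is not stated to be complete clearance, 90% lies inside the cited range, and a midpoint is not an average. Only the adjective is unsupported.

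**Conclusion.** Wrong as written; a minor correction. At 20% dropout, 150 enrolled leaves 120 evaluable patients, not the 124 that the plan requires. The shortfall against the 155 to 156 needed is 5 to 6 patients, and the power cost is about 1.3 points by the plan's apparent method.

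This rests on equal loss in the two arms and on dropout meaning a patient without a primary outcome, which is how the plan's calculation uses it. A reader might infer that the trial is materially underpowered or must enrol more. The documents do not support that: power at the planned rates stays close to 80% with the chi-squared test, and it is higher if dropout is below 20%. Low power would follow if the true PPL rate were near 83%, but that concerns a design assumption and is not an arithmetic error.

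The wording point is secondary: nothing in Section 9 shows 90% to be conservative.

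**What to change.** Change text only; keep enrolment at 150.

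- **Section 9, dropout sentence.** Replace with: *With 150 enrolled (75 per arm), 124 patients with a primary outcome are retained at up to about 17% dropout; at 20% dropout 120 (60 per arm) remain, giving about 79% power for 70% vs 90% by the pooled normal approximation (about 80% by exact chi-squared, about 73% by Fisher's exact test); if every randomised patient has a primary outcome, power is about 87% by the pooled normal approximation.*
- **Section 9, PPL rate.** Delete the word *conservative*.
- **Section 11.** Refer to the Section 9 power statement instead of asserting that power is sufficient.
- **Optional, Section 9.** Add that, with ESWL at 70%, a PPL rate of 83% (the low end of the cited range) gives about 39% power at 60 per arm and 47% at 75 per arm.

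The cost is a short amendment to two sections. The downside is that the stated power at 20% dropout becomes about 79% by the plan's apparent method instead of 80%.

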The most common AEs for PPL are expected to include pancreatitis and bleeding. The most common infectious complications are expected to include cholangitis, cholecystitis, and less likely or rare duodenoscope-related infection transmissions and perforation. No differences in the types and proportion of AEs have been found in previous studies examining EHL and LL.¹⁰

The risks of ESWL include post-ESWL pancreatitis, bleeding, infection, steinstrasse, sepsis, and rarely, perforation, pancreatic duct leak and arrhythmias. An overall AE rate for ESWL is 6.7%.²¹ The most common adverse event associated with ESWL remains pancreatitis with a meta-analysis finding a rate of 4.2%.¹⁴ Mild skin erythema and tenderness also typically occurs at the region of contact with the shockwaves and other adverse events such as bleeding and infection occur in approximately 1% of cases.³ Similarly, the primary risk of PPL is pancreatitis which in a meta-analysis was found to occur in 8.7% of cases.¹⁵ Additional risks include incomplete fragmentation of the stone requiring alternative treatment,

stone migration, inability to access stones(s), no stones, need for further procedures, loss of pancreas and/or death. Machine malfunction may occur, necessitating rescheduling. In addition, the stones might not get removed completely. In comparison, surgery, an alternative treatment modality typically consisting of either a lateral pancreaticojejunostomy or a Frey procedure, has a higher rate of adverse events. In a randomized trial comparing surgery with endoscopy, the surgical treatment arm had a 27% adverse event rate with the main adverse events including anastomotic leakage (6.8%), bleeding (6.8%), incisional hernia (4.5%), pneumonia (4.5%), and severe delayed gastric emptying (4.5%).²² Additionally, as these procedures would typically be performed as part of the management of patients with PD stones at the study sites, there are no separate research risks from the risks of standard care.

Worsening abdominal pain may occur after either of the procedures, with the potential need for prolonged observation. Abdominal pain may be related to ductal manipulation, stone mobility, or due to other adverse events.

The definition of a serious AE is any AE that results in any of the following outcomes:

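### As written, the tested overall adverse-event rate would take in a mild skin reaction listed only for ESWL, and could be driven by it

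*Combined protocol and SAP*

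**What the plan says.** Section 10.1 of the combined protocol and SAP sets a wide definition: "AEs are defined as any undesired, harmful, or pathological change in a patient as indicated by signs, symptoms, or laboratory changes". Causality is not needed, since an event counts "whether considered intervention-related or not". There is no severity floor and no exclusion for expected local effects of a procedure. For events other than pancreatitis, the mild grade in the same section covers a passing event that needs no treatment and leaves daily life undisturbed. Section 10.2 has all adverse events entered in the central system.

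Section 9 makes the rate an outcome for testing: "Secondary outcomes including adverse event (both overall and serious adverse event) rates, procedure length, and number of procedures will be compared" with a chi-square or Fisher's exact test, and "A p value <0.05 will be considered significant". The Synopsis also lists adverse events among the secondary endpoints.

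On the skin effects of shock waves, Section 10.1 says: "Mild skin erythema and tenderness also typically occurs at the region of contact with the shockwaves and other adverse events such as bleeding". It puts the latter group, which also takes in infection, at about 1%. The same paragraph states "An overall AE rate for ESWL is 6.7" per cent, and names pancreatitis, at 4.2%, as the most common ESWL event. For PPL it gives pancreatitis at 8.7% and no overall rate. Worsening abdominal pain is named as possible after either procedure. No skin-contact sign is listed for PPL.

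**The concern.** A coordinator who follows these sections to the letter would enter reddened or tender skin after ESWL as a mild adverse event. The sign belongs to one arm by the nature of the procedure, is described as usual, and has little clinical weight. Once entered, it counts the same as a case of pancreatitis in a rate of patients with any event. The overall comparison could then show mainly how often shock waves mark the skin and how diligently each of eight sites writes it down, and patients and staff know the allocation.

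The stake is a tested secondary outcome. The protocol's cited figures put ESWL at 6.7% and PPL at no less than 8.7%. Even partial recording of the skin sign could reverse that order and produce a nominally significant result against ESWL, while saying nothing about the complications that matter to patients.

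**Working it through.** **Do the rules take the sign in?** The definition has no floor, the mild grade fits the sign, all events are entered, and the tested rate has no severity threshold. Taken literally, yes. **Do the cited rates include it?** No. A sign that is usual after ESWL cannot sit inside an overall rate of 6.7%, and pancreatitis at 4.2% could not then be the most common event. The definition and the benchmark rates therefore conflict, and no sentence resolves the conflict.

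**The plan's arm size.** Section 9 assumes clearance of 70% and 90%, two-sided 0.05 and 80% power. The usual two-proportion formula gives [1.96·√(2·0.8·0.2) + 0.842·√(0.7·0.3 + 0.9·0.1)]² / 0.2² = (1.109 + 0.461)² / 0.04 ≈ 61.6, so 62 per arm, as stated. The plan then sets 75 per arm for dropout. I use 75 as given.

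**Inputs for the adverse-event test.** From Section 10.1: ESWL 6.7% without the skin sign, and PPL 8.7%. Assumed: a share *q* of ESWL patients has the sign recorded, independently of other events, and the cited rates apply per patient.

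- ESWL rate = 1 − (1 − 0.067)(1 − *q*).
- For *i* ESWL and *j* PPL patients with an event, *n* = 75 per arm and *t* = *i* + *j*, Pearson's statistic is X² = 2*n*(*i* − *j*)² / [*t*(2*n* − *t*)]. It is significant above 3.84.
- The chance of a significant result against ESWL is the sum of the binomial probabilities over all (*i*, *j*) with *i* > *j* and X² > 3.84.

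| *q* | ESWL rate | Expected patients, ESWL vs PPL | Chance of a significant result against ESWL |
|---|---|---|---|
| 0 | 6.7% | 5.0 vs 6.5 | 0.9% |
| 5% | 11.4% | 8.5 vs 6.5 | 8% |
| 10% | 16.0% | 12.0 vs 6.5 | 28% |
| 20% | 25.4% | 19.0 vs 6.5 | 80% |
| 30% | 34.7% | 26.0 vs 6.5 | 98% |
| 50% | 53.3% | 40.0 vs 6.5 | above 99.9% |

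The ESWL rate passes 8.7% once *q* exceeds 1 − 0.913/0.933 = 2.1%. Fisher's exact test gives 73% rather than 80% at *q* = 20%.

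**If the PPL rate differs.** At *q* = 10%, 20% and 30% the chance is 45%, 90% and 99.5% with PPL at 6.7%, and 11%, 57% and 92% with PPL at 12%.

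**If mild pain is recorded in both arms.** The wide definition also takes in post-procedure abdominal pain. With pain in an assumed 30% of each arm, independent of the rest, PPL becomes 1 − 0.913·0.7 = 36.1%. ESWL becomes 1 − 0.933·0.8·0.7 = 47.8% at *q* = 20% and 1 − 0.933·0.7·0.7 = 54.3% at *q* = 30%. The chances fall to 32% and 63%. With pain in 50% of each arm they are 19% and 38%. At *q* = 50% they stay high: 98% with pain at 30% and 83% with pain at 50%.

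**The case against.** The strongest reply is that the protocol does not treat the skin sign as an adverse event at all. No sentence says it enters the overall rate, the 6.7% and 4.2% figures leave it out, and the phrase about other adverse events may simply refer back to pancreatitis in the sentence before. A reader might infer from the text that the sign *is* counted and that ESWL *will* look worse. The documents do not go that far. What stands is that the cited sources left the sign out, which does not tell sites what to do in this trial, and the operative definition points the other way.

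A second reply concerns the size. The first table counts ESWL under the widest reading but holds PPL at a published pancreatitis rate from a different source. That is fair, and counting mild pain in both arms reduces the effect considerably, as shown.

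Two further readings are tempting and should not be drawn:

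- **A lower threshold for ESWL.** Section 10.1 applies a society classification to endoscopic events, but does not say that this replaces the general definition. Under Section 5.5 ESWL patients also have an ERP, so endoscopic events arise in both arms. The imbalance comes from a sign listed for one arm only.
- **A risk of early stopping.** Section 10.3 speaks of an unexpected accumulation of events. Section 10.1 ties unexpectedness to the plan's own risk information, which already discloses the skin sign. Nor is any interim significance test on adverse events specified.

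Finally, adverse events are absent from the major secondary endpoints in Section 2, and serious events are compared separately. Both points limit the importance and both stand.

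**Conclusion.** The point holds in a limited form. Followed as written, Sections 9, 10.1 and 10.2 would let a trivial sign listed only for ESWL into a tested comparison, in conflict with the event rates that the protocol itself cites. Whether this distorts the result depends on what sites record, which the plan leaves open.

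If they record the sign in 10% to 30% of ESWL patients, the chance of a significant result against ESWL is about 28% to 98% with PPL at 8.7%. At 20% and 30% recording it is 32% and 63% if pain is also recorded in 30% of each arm. Without the sign it is 0.9%. These figures rest on assumed recording rates, independence between events, 75 evaluable patients per arm and a PPL rate that is pancreatitis only. They show sensitivity and are not a forecast. The effect is confined to the overall rate: the serious-event comparison is untouched, and nothing here bears on stopping the trial.

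**What to change.** Before analysis, amend Sections 9 and 10.1 as follows:

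- **Tested endpoint.** Define it as patients with at least one procedural complication from a single list applied to both arms. The list can use the complications the protocol already names: pancreatitis of any grade, bleeding, infection, perforation, duct leak, steinstrasse and cardiopulmonary events. State for both arms alike whether post-procedure pain is on it.
- **Skin-contact effects.** Record erythema and contact tenderness on a separate line and report them descriptively.
- **Full reporting.** Tabulate all adverse events by arm and severity grade. Every event still goes to the DSMB, in line with its review of all events under Section 10.3.

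A cut-off at moderate severity is not a safe substitute. Section 10.1 grades pancreatitis without organ dysfunction as mild, so a cut-off would drop part of what the protocol calls the primary risk of PPL.

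The cost is a few sentences and one coding flag in REDCap. The small downside is that mild local effects are described and not tested. No safety data are lost.

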Subjects may withdraw from the study at any time for any reason. Subjects can also be withdrawn from the study at any time at the discretion of the investigators for breach of study protocol or emergence of an exclusion criteria (i.e. pregnancy).

The study can be stopped at any point should the Data Safety Monitoring Board (DSMB) request cessation

of the trial based on any compilation of adverse events or clear demonstration of superiority of one technique. Similarly, should the interim analysis reveal futility in that the study hypothesis is deemed unprovable within the constraints of the study, the study may be stopped. The study will also be stopped once the intended sample size goal is reached and 6-month follow-up has been obtained. Lastly, the study can be stopped should study costs exceed the allotted budget.

8. Data Collection Tool

A comprehensive system has been previously developed at this institution, and will support the data collection and reporting needs of this project which includes:

- (i) streamlining data collection from the participating centers,
- (ii) creating a secure database from which statistical analysis can be performed. Data will be stored at the University of Colorado instance of REDCap15, which resides on a local secure server. Data regarding stone clearance rates and adverse events will be entered by investigators at each center. Using an Application Programming Interface (API), data can be transferred to and from REDCap to SAS software (v.9.3, SAS Institute, Cary, NC) used to export data from REDCap to SAS to conduct analysis. SAS software interfaces seamlessly with REDCap-produced syntax files (i.e. SAS code) and SAS-ready CSV (comma separated variables) data files. Results of these analyses will be imported back into REDCap, using the API, for long-term storage, reference, and further analysis. Access to these data will be controlled by a custom module and all users of the site will be required to log in. No protected health information will be collected or displayed and data stored in our HIPAA compliant serve environment to ensure privacy.

9. Data Analysis Plan

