- 1) death, 2) life-threatening, 3) persistent or significant disability/incapacity, or 4) requires or prolongs hospitalization. Serious AEs are expected to include perforation, air embolism, and cardiopulmonary AEs associated with the use of general anesthesia, which will be used in all procedures.

Unexpected AEs will be defined as any AEs with specificity or severity which is not consistent with the current risk information in this investigational plan as formulated from prior studies investigating the trial interventions.

Grading of severity of AEs will be done in accordance to the grading system proposed by the ASGE and the revised Atlanta classification.^{20, 23} For pancreatitis, grading will be done according to the revised Atlanta classification as follows:

- 1) Mild – no organ dysfunction, 2) Moderate - transient organ failure <48 hours OR local or systemic AEs without persistent organ failure, and 3) Severe – persistent single or multi organ failure >48 hours OR present or persistent systemic inflammatory response syndrome (SIRS).

All other AEs will be classified as follows:

- 1) Mild – AE is usually transient, does not require any special treatment, and does not interfere with the patient's daily activities, 2) Moderate – AE usually introduces a low level of inconvenience or concern to the patient and may interfere with daily activities, but are usually ameliorated with simple therapeutic maneuvers, and 3) Severe – AE interrupts a patient's usual daily activity and generally requires systemic drug therapy or other intervention.

10.2 *Procedures for documentation of adverse events*

All AEs are to be reported using the centralized online data collection system. All AEs must be entered within 14 days of occurrence. A standardized reporting system will be available on the REDCap system, which will be accessible to all study members at each site. AE reporting can be done by either site PIs or research coordinators.

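### The three pancreatitis severity grades in Section 10.1 overlap: as written, SIRS without organ failure is both mild and severe

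*Combined protocol and SAP*

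**What the plan says.** Section 10.1 gives pancreatitis its own severity scale: "For pancreatitis, grading will be done according to the revised Atlanta classification as follows". The three grades are:

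- "Mild – no organ dysfunction"
- Moderate: "transient organ failure <48 hours OR local or systemic AEs without persistent organ failure"
- Severe: "persistent single or multi organ failure >48 hours OR present or persistent systemic inflammatory response syndrome (SIRS"

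Nothing in Section 10.1 or elsewhere says what to do when an event satisfies two grades.

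The same section defines an unexpected adverse event (AE) partly by whether its severity fits the known risk information. It names pancreatitis as the most common AE of ESWL (4.2%) and as the primary risk of PPL (8.7%).

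Under Section 10.2, site PIs or research coordinators report AEs. The PIs check serious AEs for seriousness, relationship and completeness, and the DSMB then confirms their findings. Under Section 10.3 the DSMB reviews all AEs.

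**The concern.** A severity scale is useful only if each event has one place on it. Here the severe grade joins its two limbs with OR, so SIRS is sufficient by itself, and the word for SIRS that is merely present removes any minimum duration. Mild looks only at organ function and is silent on SIRS. Two people applying the text correctly to the same patient can therefore record opposite ends of the scale.

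The event concerned is the complication that the protocol expects most often in both arms, and eight sites will be applying the text. With few cases expected, one or two graded differently would visibly alter a severity table by arm. The same choice can feed into whether an event counts as unexpected, and into the picture that the DSMB is given.

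**Working it through.** **Step 1. Turn the wording into tests.** Inputs are the three definitions in Section 10.1.

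- Mild: organ failure = none.
- Moderate: organ failure = transient, or a local or systemic complication with organ failure not persistent.
- Severe: organ failure = persistent, or SIRS = yes.

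Mild speaks of organ dysfunction and the other grades of organ failure. I treat these as the same thing, which is an assumption.

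**Step 2. Apply the tests to every combination.** Organ failure (3 levels) × SIRS (2) × local complication (2) = 12 combinations. Each cell lists every grade that is met.

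| Organ failure | No SIRS, no local complication | Local complication only | SIRS only | SIRS and local complication |
|---|---|---|---|---|
| None | mild | mild, moderate | mild, severe (and moderate, if SIRS counts as a systemic AE) | mild, moderate, severe |
| Transient | moderate | moderate | moderate, severe | moderate, severe |
| Persistent | severe | severe | severe | severe |

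Five of the 12 combinations meet more than one grade, and two of those five meet both mild and severe. The count of five is the same whether or not SIRS is read as a systemic AE. These are counts of logical combinations, not of patients; they do not say how often each occurs.

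**Step 3. Trace where the grade is used.**

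- Section 9 compares overall and serious AE rates. A pancreatitis case counts once in the overall rate whatever its grade. Seriousness is defined separately in Section 10.1, by the outcome of the event. Neither comparison uses the grade.
- Section 7 lets the DSMB ask for cessation "of the trial based on any compilation of adverse events or clear demonstration of superiority of one technique", and the interim text in Section 10.3 speaks of an unexpected build-up of AEs. Neither refers to grade or gives a threshold.
- The definition of an unexpected AE in Section 10.1 does use severity.
- Section 10.3 puts all AEs before the DSMB, so recorded grades can form part of what it sees.

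**Step 4. Scale.** Inputs are 75 patients per arm (Section 9) and the two pancreatitis rates (Section 10.1). The assumption is that the rates apply per randomised patient.

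- PPL: 75 × 0.087 = 6.5
- ESWL: 75 × 0.042 = 3.2 (3.15 before rounding)
- Total: 6.525 + 3.15 = 9.7, roughly 10 cases

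At the 62 per arm left after the planned dropout allowance: 62 × 0.087 + 62 × 0.042 = 5.4 + 2.6 = 8.0.

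Section 3 allows up to 4 sessions, so the total would be higher if the rates are per session. The documents do not say what share of cases would fall in the overlapping cells, so the number affected lies anywhere from 0 to all of these.

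**The case against.** The best reply is that an ordinal scale is normally read from the top down. SIRS is named under severe, mild is what remains, and a sensible grader would stop at the highest grade met. On that view only a clarifying sentence is missing. This has force and is a reason to rate the point low. But the text does not state that reading, and "local or systemic AEs without persistent organ failure" gives a grader a third defensible home for the same patient.

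It is also fair to say that the grade drives no listed test and no stopping threshold. That stands. What remains is the unexpected-AE definition and the DSMB's view of the data. Section 10 also leaves specific safety monitoring guidelines to be developed with the DSMB; if those were to use grade, the overlap would carry into them.

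Three stronger readings are tempting, and the documents do not support them:

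- **That unblinded sites will bias the grades.** Sites report AEs, the investigator knows the allocation (Section 5.3), and the only blinded assessment described is of stone clearance images (Section 5.5). But the documents do not name who assigns the grade. PI and DSMB review exists, although grade is not on the PIs' list of checks, and Section 12 provides training and quarterly calls. Bias is possible; neither its presence nor its direction is shown.
- **That the text departs from the classification it cites.** That source is not part of the documents, so this cannot be judged. The fault lies in the three definitions as the protocol prints them.
- **That two grading systems compete for pancreatitis.** Section 10.1 does say "All endoscopic AEs will be defined and classified as recommended by the American Society for Gastrointestinal Endoscopy (ASGE", but for severity it then assigns pancreatitis specifically to the revised Atlanta scale. The overlap arises within that scale.

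**Conclusion.** The point holds, as a minor error in the text. The pancreatitis grades are not mutually exclusive: SIRS without organ failure is mild and severe, and arguably moderate; a local complication without organ failure is mild and moderate; transient organ failure with SIRS is moderate and severe. No precedence rule resolves this.

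The reach is limited to severity reporting, the unexpected-AE call and the DSMB's view, for an unknown share of about 10 pancreatitis cases on the per-patient assumption. The primary endpoint, the overall and serious AE comparisons and every stated stopping provision are unaffected. The overlap itself follows from the wording alone; only its scale depends on assumed rates.

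**What to change.** In Section 10.1, reconcile the three definitions so that each combination of organ failure, SIRS and local or systemic complication falls in exactly one grade, and add a sentence that the highest grade met applies. Adding that sentence to the present text would by itself place every case with SIRS in severe, so the investigators should confirm that this is what they intend or amend the definitions; which grade is clinically right is for them to settle. Use one term for organ dysfunction and organ failure, or define both.

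Apply the revised text to any pancreatitis events already graded, so that the final table uses one rule throughout.

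The cost is a short edit and re-grading of a few events at most. No endpoint, treatment or sample size changes.
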